Exclusion criteria: Individuals will be excluded based on a self-reported history of (1) unstable or significant current medical condition (recent heart attack or other heart conditions including high blood pressure); (2) severe immune system disorders (uncontrolled HIV/AIDS,

unstable multiple sclerosis symptoms), (3) respiratory diseases (exacerbations of asthma or COPD, require oxygen, require oral prednisone), kidney (dialysis) or liver diseases (cirrhosis) or any medical disorder/medication that may affect participant safety, study outcomes, or biomarker data will be excluded. Individuals who report more than 25 days of alcohol use in the past 30 days or more than 15 days of marijuana use in the past 30 days will be excluded. Individuals with past month use of cocaine, opioids, benzodiazepines, and methamphetamine will be excluded. Participants with current, diagnosed psychiatric conditions will also be excluded. Participants will be excluded for any use of an ENDS product in the past 30 days, or any report of daily use of ENDS for a week or more. Regular use of ENDS is excluded as we are interested in understanding the effect of these liquids on smokers who are relatively naïve to ENDS use so that prior experience does not obscure laboratory experience of use.

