
Smoking/Vaping" Lab Sessions: The sessions will occur no more than 2 days per week and will be separated by at least 48 hours. The approximate total time that participants will be in the laboratory is 12.5 hours (30 minutes for screening and 12 hours for 3 4-hour long sessions). This does not include the 12 hours before each session that we ask participants to abstain from smoking.

Note: Most questionnaires are completed via computer in the laboratory. The only exception for subjects is the glms, administered via pen & paper. EnrollmentInformation, SessionInformationSheet, BiochemicalTestResults, and the SaltStudySessionSheet are completed by Research Staff.

The session will begin with the participants' self-report of their last cigarette, CO expired air testing, and cotinine saliva testing. If the last cigarette smoked was within 12 hours or CO is above 10 ppm, the participant will be told they need to reschedule for another time and must abstain for 12 hours before the next visit. If there are 2 consecutive sessions indicating non-compliance, the participant will be disqualified from the study and paid as outlined in the compensation section. If participant's tobacco abstinence is bioverified, they will begin a 1-hour waiting period to ensure nicotine abstinence. Nicotine abstinence (e.g., ENDS, NRT) unfortunately cannot be bioverified quickly. Blood analyses at VCU CSTP have indicated high rates of lack of compliance, but much better data in protocols that involve a 1-hour waiting period in the lab. After this waiting period, the participant will continue on with physiological equipment attachment and catheter insertion. Physiological equipment (Criticare 506DNP3R, includes blood pressure cuff and SpOv2 sensor) will continuously measure BP/HR by trained Research Assistants or the study PI.

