The product that is used will be based on pre-established Latin-square order procedure (similar to random assignment) to avoid any order effects. For example, a participant may use the Subox Mini C with 18 mg regular (unprotonated) nicotine the first session, own brand cigarette the second session, and Subox Mini C with protonated nicotine on the last session. Participants will use a different product each session and use all 3 products by the completion of the study.

The cigarette will be purchased at a local retailer based on the participant's self-report in the baseline questionnaire of cigarette brand typically smoked. Smokers are often very loyal to a brand, so this will allow for a control condition of understanding standard reactions to cigarette smoking. The ENDS device will be a Subox Mini C, as recommended by VCU collaborators, who have had prior and current success using this device. The Subox will include a solution with either 18 milligrams/milliliter (mg/mL) of nicotine salt (protonated nicotine) or 18 mg/mL of regular (unprotonated) nicotine. The flavor will match their usual brand of cigarettes (tobacco-flavored or menthol-flavored).

Using a stopwatch, research assistants will instruct participants to take one puff of the tobacco product (cigarette or ENDS) every 30 seconds for 5 minutes. Participants will also complete another set of questions involving evaluation of the product consumed and nicotine withdrawal symptoms. Next, participants will be given 90 minutes to use *ad lib*, i.e., as much as desired. Smoking/vaping sessions will be videorecorded to allow for measurement of puff topography (puff duration, inter-puff interval, etc.). Final questionnaires will be completed. The participant will then be reminded of their schedule for the next session, if another session remains.

Experimental session timeline (approximate times):

- Participant arrives, CO test to confirm tobacco abstinence
- 1-hour waiting period (to help ensure nicotine abstinence), then the rest of the session will begin, as described below
- 0 Hr 0 min - Attach physio equipment, insert catheter, begin questionnaire administration
- 0 Hr 30 min - record Carbon Monoxide
- 0 Hr 35 min - 10 puffs from product (30s inter-puff interval)
- 0 Hr 45 min Record Carbon Monoxide, 2nd set of questionnaire administration

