used for each dependent variable. There are three within-subject tobacco products (own-brand cigarette, ENDS with unprotonated nicotine, ENDS with protonated nicotine) and four within-subject time points (pre-use, post-directed 10 puff session, pre-*ad lib* use session, post-*ad lib*). Three (condition) x four (time) repeated measures ANOVAs will assess plasma nicotine and heart rate (HR). Questionnaire items (or craving factors) will be examined individually using separate ANOVAs. Analyses conducted on the Hughes-Hatsuhashi Withdrawal scale, the Tiffany Drobis Questionnaire of Smoking Urges, and the Direct Effects of Nicotine (DEN) have 4 levels of time. The Direct Effects of E-cigarettes scale, unlike the DEN, only assesses reactions to the tobacco product and thus will have only 2 levels of time. Videorecordings will be evaluated via established methodology (Blank et al., 2009).

Any violations of sphericity will be adjusted using Huynh-Feldt corrections. In order to maintain statistical power and limit type 1 error for plasma nicotine, HR, and subjective effects, planned contrasts (paired samples *t*-tests) will be conducted across conditions at the two time points immediately after each use bout (e.g., each post-use session). At these two post-use timepoints, the mean value for each outcome measure in the protonated nicotine condition will be compared to the corresponding mean values in the unprotonated nicotine and cigarette conditions. Because these comparisons are non-orthogonal, a Bonferroni correction will be applied (Keppel, 1991).

References

CDC, 2011. Quitting smoking among adults--United States, 2001-2010. *MMWR Morb Mortal Wkly Rep* 60, 1513-1519.

Cohen, J., 1992. A power primer. *Psychological bulletin* 112, 155.

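### The product orders are not listed and no order term is planned; six orders plus a first-ENDS term would protect the protonated-unprotonated contrast at almost no cost

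*Combined protocol and SAP*

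**What the plan says.** Under Product consumption: "The product that is used will be based on pre-established Latin-square order procedure (similar to random assignment) to avoid any order effects". One example order is given: "regular (unprotonated) nicotine the first session, own brand cigarette the second session, and Subox Mini C with protonated nicotine on the last session". The number of orders, the list of orders and the number of participants per order are not stated.

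Data Analysis plans product by time repeated measures ANOVAs, where time means the four measurement points within a session. The paired t-tests that compare protonated nicotine with each of the other two products "will be conducted across conditions at the two time points immediately after each use bout", with a Bonferroni correction. No session, order or sequence term appears there or elsewhere.

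Three other statements bear on the point:
- Exclusion criteria: "Participants will be excluded for any use of an ENDS product in the past 30 days". The reason given for excluding regular ENDS users is "so that prior experience does not obscure laboratory experience of use".
- Lab sessions: "The sessions will occur no more than 2 days per week and will be separated by at least 48 hours".
- Lab sessions, on losses after sessions have begun: "If there are 2 consecutive sessions indicating non-compliance, the participant will be disqualified from the study". No rule says how a lost participant's order is refilled.

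**The concern.** Each participant uses the same ENDS device in two of the three sessions. Before the second of these, a smoker who is new or nearly new to ENDS has already had 10 directed puffs and 90 minutes of free use, possibly only 48 hours earlier. The protocol's own case for near-naive participants makes it plausible that the second ENDS session differs from the first, whichever liquid is used.

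A Latin square balances each product over sessions 1, 2 and 3. That does not balance which ENDS comes first. Protonated against unprotonated nicotine is the first comparison named in the research questions. If one liquid usually comes first, part of any familiarity or novelty effect would be credited to nicotine form. If the two liquids come first equally often, the same effect widens the error term of the planned t-test and costs power.

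**Working it through.** **Inputs.** From the documents: 30 completers, three products, three sessions, paired t-tests, a large target effect. Assumed, because the documents do not give them: d, the change from first to second ENDS session, at 0.25, 0.5 and 1.0 SD of the paired difference; 0.8 SD for the large effect; 0.53 SD as a smaller effect (80% power at n = 30 and 5%); a Bonferroni level of 2.5% (two contrasts) or 1.25% (two contrasts at two time points).

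**The plan's figure.** N = 30 cannot be reproduced exactly, since alpha, power and correlation are not stated. It is consistent with its aim: a paired t-test with n = 30 has power 98.9%, 97.4% and 95.0% for 0.8 SD at 5%, 2.5% and 1.25%.

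**Orders.** Let C = cigarette, S = protonated, R = unprotonated. Only two 3x3 Latin squares exist:
- CSR, SRC, RCS (contains the protocol's example): S before R in 2 of 3 orders, or 20:10.
- The other square: S before R in 1 of 3 orders, or 10:20.

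All six orders with five completers each give 15:15, and each product still falls 10 times in each session.

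**Bias.** S - R moves by -d when S comes first and by +d when R comes first. In the example's square the mean shift is (10d - 20d)/30 = -d/3. A session term alone does not remove it. With six orders it is (15d - 15d)/30 = 0.

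**Type I error, single square, plain paired t-test (simulated, no other session effect):**

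| d | bias (SD) | at 5% | at 2.5% | at 1.25% |
|---|---|---|---|---|
| 0.25 | 0.08 | 6.5% | 3.4% | 1.8% |
| 0.5 | 0.17 | 10% | 5.5% | 2.9% |
| 1.0 | 0.33 | 17% | 9.1% | 4.5% |

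**Six orders, plain paired t-test.** The mean is unbiased, but the variance of the difference rises from 1 to about 1 + d², that is 1.25 at d = 0.5 and 2 at d = 1.0. Type I error at 2.5% drops to about 1.3% and 0.2%, and power drops with it.

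**Power at 2.5%:**

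| Orders and analysis | d | 0.8 SD | 0.53 SD |
|---|---|---|---|
| Paired t-test, either order list | 0 | 97% | 70% |
| Single square, paired t, bias against the effect | 0.5 | about 80% | 28% |
| Single square, paired t, bias with the effect | 0.5 | over 99% | 88% |
| Six orders, paired t | 0.5 | 95% | 60% |
| Six orders, paired t | 1.0 | 83% | 34% |
| Six orders, first-ENDS term | any | 97% | 70% |

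The gains in the third row are partly bias. With six orders, d = 0.5 and a further linear change of 0.5 SD from session 1 to session 3, power is 89% and 43% without the term and 97% and 69% with it.

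**Cost of the term.** Its variance factor for S - R is 1/(1 - m²), where m is the difference between the two order-group sizes divided by 30. At 15:15, m = 0 and the factor is 1. At 20:10, m = 1/3 and the factor is 1.125. With six orders the only cost is one degree of freedom (29 to 28), under 0.2 points of power when d = 0.

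**Why the term alone does not rescue a single square.** Let p1, p2, p3 be session effects. In the example's square, the S-first group averages [(p1 - p2) + (p2 - p3)]/2 = (p1 - p3)/2, and the R-first group gives p3 - p1. The mean of the two is (p3 - p1)/4, so a quarter of any session 1-to-3 change enters. A change of 0.5 SD with d = 0 gives type I error 9.5% at 5%.

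**Completer imbalance.** If 36, 40 or 50 eligible people were assigned 1:1 and 30 completed at random (an assumption), a split of 18:12 or worse has probability 1.9%, 6.5% or 15%. At 18:12 the bias is (18 - 12)d/30 = d/5.

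**The case against.** The strongest reply is that no defect is shown. A Latin-square procedure can mean a pair of squares, which is all six orders; 30 divides by six, and the example order belongs to either scheme. With six orders the planned test is valid, and for the stated large effect it loses little: 97% to 95% at d = 0.5. This stands, and it is why the point is an improvement and not an error.

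The size of d is unknown, and the stated rationale for exclusion concerns regular ENDS use, not one supervised session. That also stands: d is an assumption throughout.

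The 10% and 17% error rates are at an uncorrected 5%. If Bonferroni covers four comparisons, single-square type I error stays below 5% for every d considered, though it still exceeds the nominal 1.25% more than twofold at d = 0.5. The 0.53 SD effect is smaller than the trial's target.

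Finally, an 18:12 split barely changes type I error (5.3% at a nominal 5% with d = 0.5). Power for 0.8 SD at 2.5% does fall, from 97% to 88%, when the bias opposes the effect. The first-ENDS term removes d/5, so a replacement rule is secondary once the term is in place.

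None of this argues for leaving the orders unstated or the term out.

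**Conclusion.** The concern holds as a cheap improvement that should be made; confidence is medium. The protocol promises to avoid order effects without giving the orders, and the analysis contains nothing to handle them. Under a single square the main ENDS contrast carries bias d/3. Under six orders it is unbiased but loses power when d is not zero. Six orders with a first-ENDS term is better under either reading when d is not zero, and costs almost nothing when d is zero. The sizes rest on assumed values of d, effect and Bonferroni family. N = 30 is not in question.

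**What to change.** 1. List the orders. Use all six with five completers each, assign order at random once eligibility is confirmed at the screening visit, and replace a non-completer within the same order.
2. For protonated against unprotonated, analyse the within-person difference at each of the two post-use time points with a term for which ENDS came first. The estimate is the average of the two order-group means. Keep this contrast's own error term and the Bonferroni correction.
3. Keep the protonated-cigarette paired t-test as planned. If a joint model is preferred, code the ENDS term -1/2 (first), +1/2 (second) and 0 (cigarette). With 0/1 coding plus session, that contrast becomes first-use ENDS against cigarette, and its variance rises 45% (0.0667 to 0.0967 in units of the residual variance). Centred coding keeps 0.0667.
4. If a single square is already fixed, do not add the first-ENDS term alone. Fit session and the centred ENDS term together, in a joint model that includes the cigarette sessions.

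**Cost.** Six orders need a revised order list, a replacement rule and a short analysis paragraph, with no extra participants or visits. If a single square must stay, the two terms raise the variance of the ENDS contrast by 25% (0.0667 to 0.0833). Power at 2.5% is then 94% instead of 97% for 0.8 SD and 62% instead of 70% for 0.53 SD, assuming equal error variance across products.

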Electronic nicotine delivery systems (ENDS) aerosolize liquid nicotine that the user inhales in a process similar to cigarette smoking. ENDS are considered tobacco products under US law as long as they include plant-derived nicotine and are not marketed with therapeutic intent (Sottera, Inc v. FDA, 627 F.3d 891, DC Cir. 2010). Although many ENDS deliver nicotine, flavor additives, and other potentially addictive or harmful chemicals, they do not burn tobacco, a process that yields an estimated 7000 chemicals, including at least 70 carcinogens (Douglas et al., 2018; US Department of Health and Human Services, 2014). Former smokers who use ENDS rate ENDS as less risky, better tasting, more satisfying, and better at reducing craving, negative affect, and stress than FDA-approved NRT (Harrell et al., 2015). Smokers who switch completely to ENDS substantially reduce their exposure to numerous toxicants and carcinogens present in combustible cigarettes, thus improving their health in the short term (Goniewicz et al., 2014; Harrell et al., 2014). In a 2018 report reviewing the scientific evidence, the National Academies of Sciences Engineering and Medicine (NASEM) determined there is “conclusive evidence that completely substituting e-cigarettes [ENDS] for combustible tobacco cigarettes

reduces users' exposure to numerous toxicants and carcinogens present in combustible tobacco cigarettes (NASEM, 2018)."

From 2015-2017, an ENDS marketed as "Juul" went from being a little-known brand with low sales into being the largest retail ENDS brand in the US, lifting sales of the entire ENDS category (Huang et al., 2018). Juul differs from many other ENDS in the use of nicotine salts (protonated nicotine). Nicotine salts may play an important role in the effects of Juul, but this has not been systematically assessed. Preliminary research on Juul devices suggest they may be safer than other ENDS devices (Reilly et al., 2018), which, as noted previously, appear substantially safer than cigarette smoking (National Academies of Sciences Engineering and Medicine, 2018).

Research questions: Does the use of nicotine salts (protonated nicotine) differ from regular (unprotonated) nicotine or own-brand cigarette in: 1) cigarette craving reduction; 2) withdrawal symptoms reduction; and 3) appeal as measured on a variety of dimensions regularly assessed for tobacco products?

Study design:

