Self-report measures for tobacco product evaluation: Self-report measures were based on established batteries used by VCU CSTP and others (e.g., (Spindle et al., 2018). Four of the five measures use a computerized visual analog scale (VAS) containing a word/phrase in the middle of a horizontal line with "not at all" on the far left and "extremely" on the far right. Participants will record responses by clicking on any point on the line, with scores expressed as a percentage of total line length (i.e., 0-100). Nicotine abstinence symptoms will be assessed via the Hughes-Hatsukami withdrawal scale (Hughes and Hatsukami, 1986). Craving will be assessed by the Tiffany Drobis-QSU Brief consisting of 10 items involving 2 factors: (1) intention to smoke a cigarette and (2) anticipation of relief from abstinence symptoms by smoking (Tiffany and Drobis, 1991). Additional VAS questionnaires will include the Direct Effects of Nicotine (Cappelleri et al., 2007; Evans et al., 2006) and the Direct Effects of ECIG-use scales (10 items; adapted from (Foulds et al., 1992; Pickworth et al., 1994). The fifth questionnaire (the general labeled magnitude scale, gLMS; adapted from (Green et al., 1993) will assess the flavor sensation, harshness/irritancy, and throat hit provided by the tobacco product using a category-ratio scale with 7 semantic labels ranging from (0) "no sensation" to (100) "strongest imaginable sensation of any kind." The questionnaire will be administered via pen and paper after the two tobacco product use bouts in each session.

An additional questionnaire will assess changes in expectancies after product use. The questionnaire uses items from the Smoking and Vaping Consequences Questionnaires – Brief (Hendricks et al., 2015) as well as the Comparing E-Cigarettes and Cigarettes questionnaire (Hersberger et al., 2017). Responses range from "completely unlikely" to "completely likely". Depending on which product was assigned for the session, either the vaping (VCQ-B) or smoking (SCQ-B) items will be used.

Product consumption: The participant will use one of the following three products:

- Own brand cigarette
- ENDS: Subox Mini C with 18 mg nicotine salt (protonated)
- ENDS: Subox Mini C with 18 mg nicotine regular (unprotonated)

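### The protocol describes no masking of the two e-liquids, which share device, strength and flavour, so the salt-versus-regular contrast on self-reported outcomes is open to expectancy bias

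*Combined protocol and SAP*

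**What the plan says.** The research questions ask whether protonated nicotine differs from the regular form, or from the cigarette the participant usually smokes, on three counts: "1) cigarette craving reduction; 2) withdrawal symptoms reduction; and 3) appeal as measured on a variety of dimensions regularly assessed for tobacco products".

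The instruments are described under the self-report measures and are completed by the participant. For withdrawal: "Nicotine abstinence symptoms will be assessed via the Hughes-Hatsukami withdrawal scale". Craving uses a brief smoking-urges questionnaire, and product evaluation uses further visual analogue scales and a labelled magnitude scale on paper. For the visual analogue scales, "Participants will record responses by clicking on any point on the line, with scores expressed as a percentage of total line length", that is, 0 to 100.

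On the products: "The ENDS device will be a Subox Mini C, as recommended by VCU collaborators", and "The Subox will include a solution with either 18 milligrams/milliliter (mg/mL) of nicotine salt (protonated nicotine) or 18 mg/mL of regular (unprotonated) nicotine". Flavour is tobacco or menthol according to the participant's usual brand, so it is the same for both liquids within a person. A pre-established Latin square sets the order of the three products.

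The data analysis section plans paired t-tests of the salt condition against each of the other two, at the two post-use time points, with a Bonferroni correction. Plasma nicotine and heart rate get the same contrasts.

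Neither the order paragraph, the product description nor the session timeline mentions coded containers, a separate preparer, or masking of anyone. The only appearance of the word blind is in the title of a cited reference.

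**The concern.** Salt versus regular nicotine is the comparison that motivates the study. By fixing device, strength and flavour, the design has already removed the most obvious cues that tell the liquids apart, so masking this pair is feasible. The outcomes behind all three research questions are ratings, which can move with what a person believes they are using.

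The protocol already treats such influences as relevant. It excludes recent or regular ENDS users "so that prior experience does not obscure laboratory experience of use", and it measures expectancies at baseline and after use. It does not, however, describe any control over knowledge of the liquid, or any question about which liquid the participant believed was in the device.

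If a shared belief about one liquid shifts its ratings, that shift enters the estimated difference in full. It could produce a difference where none exists, or hide a real one if it runs the other way.

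**Working it through.** **Does any existing design feature remove the bias?**

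- *Latin square.* It balances the session in which each product is used. A belief about a liquid travels with that liquid into whichever session it falls, so balancing order leaves it in place.
- *Within-subject comparison.* It cancels traits that are constant across a person's sessions. A belief that differs between the two liquids is not constant, so it stays in the paired difference.
- *Bonferroni correction.* It lowers the significance threshold but does not move the estimate.

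**Illustration of size**

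The protocol gives no figure for this bias, so there is none to reproduce. Its only relevant number is the 30 completers in the sample-size paragraph, said to allow detection of a large effect. That is consistent with a paired t-test: if large is taken as 0.8 SD of the paired difference, power at n = 30 is 98.8%, 97.4% and 95.0% at two-sided alpha 0.05, 0.025 and 0.0125. It cannot be reproduced exactly, because alpha, power, correlation and a numeric effect size are not stated.

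Inputs:

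- n = 30, so df = 29 (protocol).
- No true difference between the liquids (assumed).
- Paired-difference SD of 20, 25 or 30 points on the 0 to 100 scale (assumed).
- Expectancy shift of 5 or 10 points, in one direction (assumed).
- Per-contrast alpha. The protocol states neither the Bonferroni family nor the overall level. With an assumed overall 0.05, two comparisons at two time points give 0.05/4 = 0.0125, and two comparisons give 0.05/2 = 0.025. The two-sided critical t values are 2.663 and 2.364.

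Formulas: d = shift/SD; noncentrality = d × √30 = d × 5.477. The false-positive rate is P(T > t crit) + P(T < −t crit), where T is noncentral t with 29 df.

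| Shift | SD | d | Noncentrality | Rate at 0.0125 | Rate at 0.025 |
|---|---|---|---|---|---|
| 5 | 20 | 0.250 | 1.369 | 11.5% | 17.6% |
| 5 | 25 | 0.200 | 1.095 | 7.2% | 11.7% |
| 5 | 30 | 0.167 | 0.913 | 5.2% | 8.7% |
| 10 | 20 | 0.500 | 2.739 | 53.7% | 64.7% |
| 10 | 25 | 0.400 | 2.191 | 33.6% | 44.2% |
| 10 | 30 | 0.333 | 1.826 | 22.1% | 31.1% |

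With no shift the rate equals the alpha in each column, 1.25% or 2.5%. The noncentrality grows with √n, so enrolling more people would raise these rates.

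**The case against.** The best counter-argument is that silence is not a description of open-label use, and several stronger readings fail for that reason.

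- *A reader might infer that the liquids are given unmasked.* The text does not say so, and it nowhere says that participants are told which liquid is loaded. The consent form, which might say what they are told, is not part of the text reviewed. The post-use expectancy items are chosen only by vaping or smoking, which would fit participants knowing only the product class, though it does not show it.
- *A reader might infer that research assistants who know the order fill the device and collect the ratings.* The protocol says they time and instruct the puffs. It does not say who fills the tank, who holds the order list or whether session staff see it. Participants enter most ratings themselves by computer, which weakens the staff route.
- *A reader might infer that a salt-versus-regular difference could not be told apart from expectation.* That goes too far. Plasma nicotine and heart rate are tested with the same contrasts at the same time points and are less open to expectancy, and measured expectancies also help interpretation. None of these replaces masking, and the research questions name neither plasma nicotine nor heart rate.

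Three further points stand in part. Smokers with little ENDS experience may hold no strong shared belief about nicotine salts, and beliefs that point in different directions would mainly add variance. Harshness and throat hit, which are themselves outcomes, may reveal the liquid even under masking. And masking does nothing for the cigarette half of each research question.

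These limit the size and scope of the point. They do not supply the missing procedure: staff who followed the text exactly would have no instruction to mask, and masking that is not written down cannot be relied on or verified.

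**Conclusion.** The point holds for salt versus regular nicotine on the self-reported scores. It is a gap in the design as described, and more than a missing detail, because the contrast is planned, can be masked, and rests on participant ratings.

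How large the bias would be is unknown. The rates in the table show how sensitive a contrast with 30 pairs would be to a one-directional shift; they say nothing about how likely such a shift is. They rest wholly on the assumed shifts, SDs and alpha levels. The point disputes no figure in the protocol and does not change the sample size.

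**What to change.** Amend the product consumption section as follows:

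1. Existing staff who are not running that session fill identical bottles or tanks and label them by code.
2. Participants and session research assistants are told only that the product is an e-cigarette or the own-brand cigarette. This is enough to choose the vaping or smoking expectancy items, and the vital-sign rules do not depend on the liquid.
3. The code is kept apart from the session sheets until data cleaning, outlier decisions and video scoring of the ENDS sessions are finished.
4. One end-of-session question asks which liquid the participant thinks was used.
5. The text states that the cigarette condition is unmasked.

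If the sponsor intends open-label use of the liquids, the protocol should say so and discuss the limitation for the rated outcomes.

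The cost is a protocol paragraph, labelling by existing staff, one added question and a code list to maintain. The main downside is that harshness or throat hit may partly unmask the liquids; the product-guess question would show how far.
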